4.12.2 ECG Analysis

Intensive cardiac assessments will be performed using food effects on the adjudicated ECGs to establish assay sensitivity. Analysis of drug related QT/QTc interval changes relative to plasma PK concentrations will be conducted on all dose regimens. The principles of this analysis follow the statistical methods described by Garnett et al., 2018[2]. The ECG utilised for this analysis require adjudication by qualified cardiologists in accordance with principles set out in the International Council for Harmonisation (ICH) E14 guideline and subsequent Q&A documents. All ECG recordings are in triplicate and will be compliant with the correct recording and manual adjudication of ECG in thorough QT/QTc studies.

QT Heart Rate Correction

To ensure robustness of the QTcI correction methodology, Holter/telemetry data will be used to extract QT:RR pairs at a wide range of HR values and a sufficient sample size (ideally > 400 pairs). The quality of the extracted ECGs is confirmed by excluding sections with arrhythmia, abrupt changes in heart rate (ideally stable HR for ≥ 1.5 minutes) and artefacts.

QTc will be plotted against RR interval to assess the suitability of the primary correction method.

For each subject, QT:RR pairs from Day -1 will be ranked based on the RR values (slowest to fastest heart rate). The QTcI formula will be derived using only data points with odd ranks (e.g., 1st, 3rd, 5th ranked pairs), while the data points with even ranks (e.g., 2nd, 4th, 6th ranked pairs) will be used to validate the QTcI formula and assess its performance compared to QTcF. This ranking approach ensures a good range of RR values for both determining and validating the QT correction method.

A linear mixed-effects model will be fitted using the data with odd ranks (where QTcI is derived). This model analyses the relationship between log-transformed QT and log-transformed RR, considering both fixed effects (common correction) and random effects (individual variations) for intercept and slope. The individual correction exponent for each subject is then calculated by adding the fixed and the random slope estimated by the model.

The observed ΔQTc versus concentration will be presented. In addition, a decile plot as described in the White Paper by Garnett et al., [2] will be presented with the partial residual with respect to concentration as dependent and concentration as independent variable.

The appropriateness of the model used will be investigated. In particular, this includes the absence of a delayed C-QTc effect and any relevant deviations from linearity. Presence of a delayed effect will be investigated by a simultaneous plot of $\Delta\Delta QTc$ and the mean concentration, where $\Delta\Delta QTc$ will be derived as described in 4.12.1 above. Note that a delayed effect will be a problem only if the maximum of $\Delta\Delta QTc$ (Umax) is later than the Tmax by 1 hour or more.

Deviations from linearity will be judged from the treatment intercept and the diagnostic plots. A significant treatment intercept will be taken as an indicator for inappropriateness of the model.

Investigation of C-QTc Hysteresis

C-QTc hysteresis will be assessed visually, by presenting plots of mean $\Delta\Delta QTc$ at each post-dose time point and the corresponding noribogaine plasma concentrations, in a temporal order by dose.

The presence of hysteresis may be established if any of the hysteresis plots shows a relevant counterclockwise loop.

Assessment of Secondary ECG endpoints

The ECG Heart rate (HR) and the RR, PR and QRS intervals will be summarised using descriptive statistics and change from baseline analysis.

If a change in HR of 10 bpm or more is observed a formal statistical analysis, including central tendency (by timepoint) and Concentration-HR (C-HR) analysis will be performed.

Overall interpretation (normal/abnormal) and key ECG diagnostics will be summarised by treatment group and presented in shift tables.

Assay sensitivity

The anticipated effect of the meal at 4 hours after drug administration on Days 1 and 8 will be used to show assay sensitivity. This meal is expected to produce a shortening of mean QTc by up to 5 ms at 2 to 4 hours after its ingestion (6h to 8h timepoints). This shortening will be investigated by looking at the contrasts of the time effect comparing the average of the last two preprandial timepoints to each of the 6h to 8h timepoints.

4.12 C-SSRS and MEQ30

The questionnaire data for Columbia-Suicide Severity Rating Scale (C-SSRS) and Mystical Experience Questionnaire-30 (MEQ30) will be listed by treatment and participant. The MEQ30 will be summarised by presenting descriptive statistics for the total score and each of the four factors (Mystical experience, Positive Mood, Transcendence of Time and Space, Ineffability).

4.14 Holter and Telemetry

Holter and telemetry start/end date-times with evaluations will be listed.

Statistical Analysis Plan

4.15 Meals

Meal dates and times with consumption grade will be listed by treatment and subject, ordered by visit and meal times.

4.13 Pharmacokinetic Data

Non-compartmental analysis will be used for estimation of pharmacokinetic parameters.

The following pharmacokinetic parameters will be calculated for noribogaine:

Table 5: Evaluation of Pharmacokinetic Parameters

C_{\max}	Maximal plasma concentration (Day 1 and Day 8)
t_{\max}	Time at which the maximum plasma concentration occurs (Day 1 and Day 8)
C_{12}, C_{24}	Trough concentration prior to next dose
AUC_{0-12}	Area under the plasma concentration curve from time zero to 12 hours (Day 1 and Day 8)
AUC_{0-24}	Area under the plasma concentration curve from time zero to 24 hours (Day 1 and Day 8)
AUC_{last}	Area under the plasma concentration curve to the last measurable concentration
$AUC_{0-\infty}$	Area under the plasma concentration-time curve from time 0 extrapolated to infinite time (Day 1 and 8)
$\%AUC_{\text{extrap}}$	Percentage of AUC that is due to extrapolation from t_{last} to infinity $((AUC_{0-\infty} - AUC_{0-t_{\text{last}}})/AUC_{0-\infty}) \times 100$ (Day 1 and 8)
ARC_{\max}	Accumulation ratio based on C_{\max} after the first and the last dose (C_{\max} Day 8/ C_{\max} Day 1)
$ARAUC_{\tau}$	Accumulation ratio based on $AUC_{0-\tau}$ (AUC_{τ} Day 8/ AUC_{0-12} or $0-24$ on Day 1)
$ARC_{\text{trough}2},$ $ARC_{\text{trough}3},$ $ARC_{\text{trough}4},$ $ARC_{\text{trough}5},$ $ARC_{\text{trough}6},$ $ARC_{\text{trough}7},$	Accumulation ratio based on C_{trough} on days 2-7 (C_{trough} on multiple dose day/ C_{trough} on single dose day)

Statistical Analysis Plan

λ_z	Terminal elimination rate constant obtained from linear regression of time vs log-concentration during the terminal elimination phase; using at least three time-points during the terminal elimination phase (Day 1 and Day 8)
$t_{1/2}$	Terminal elimination half-life (Day 1 and Day 8)
CL/F	Plasma clearance after extravascular administration calculated as Dose/AUC _{tau} (Day 8)
Vz/F	Apparent Volume of distribution after extravascular administration; calculated as Dose/(\mathbf{\lambda}_z * AUC _{0-inf})(Day 1, EDay 8)
Ae	Amount excreted in the urine during dosing interval (mass units)
Cum Ae	Cumulative amount excreted (mass units)
Fe	Fraction of dose excreted in urine over the collection interval; calculated as (cumulative Ae/dose)*100 (%)
Clr	Renal Clearance; calculate as Cum Ae/AUC (over equivalent interval)

Dose normalised PK parameters will be calculated as follows:

Dose normalised C_{max} = C_{max} /Dose

Dose normalised AUC_{0-12} = AUC_{0-12} /Dose

Dose normalised AUC_{0-24} = AUC_{0-24} /Dose

Dose normalised AUC_{0-inf} = AUC_{0-inf} /Dose

The individual plasma concentration data, and the actual time for noribogaine administration and blood sampling will be used in the derivation of the PK parameters. If there is any doubt in the actual time a sample was taken, then the scheduled time will be used.

AUC_{0-t} and AUC_{0-inf} will be calculated using the linear trapezoidal linear/log interpolation method, applying the linear trapezoidal rule up to C_{max} and the log trapezoidal rule for the remainder of the curve. Samples below the lower limit of quantification (LLOQ) prior to the C_{max} will be set to zero. Samples with concentrations below LLOQ after C_{max} will be set to 'missing' and omitted from the analysis. Other pharmacokinetic parameters will be calculated according to standard equations.

In the determination of λ_z (and AUC_{0-inf}), the following conditions should be met:

- A minimum of at least 3 data points in the terminal elimination phase, in which C_{max} is not included;
- The Adjusted R-squared should be ≥ 0.8 , and

- %AUCextrap < 20%.

If these conditions are not met, the PK parameter will be flagged in the listings (together with those dependent on λ_z , such as $t_{1/2}$, CL/F and V_z/F) and they may be excluded from the summary statistics. The decision to include these parameters will be based on the decision of the Sponsor with input from the pharmacokineticist. The following flags/footnotes may be applied to the PK parameters:

Flag	Footnote
a	Adjusted R-squared of regression was <0.8
b	Extrapolated portion of $AUC_{0-\infty}$ >20%
c	Insufficient post- C_{max} data points for estimation of lambda-z
d	Regression line could not be fitted

If plasma concentrations are all below the limit of quantification (BLQ), then PK parameter estimation and all subsequent statistical summaries will not be possible.

Whole blood to plasma concentration ratios will be determined on Day 1 at 1 hour, 2 hours and 6 hours.

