## **1. INTRODUCTION**

### **1.1. Background**

Noribogaine is being developed as a treatment for alcohol use disorder based on accumulated knowledge of the pharmacology and toxicology of noribogaine which has been shown to have efficacy in animal models of alcohol addiction .

Alcohol addiction encompasses the dysregulation of multiple central nervous system pathways involved in executive function leading to excessive consumption of alcohol, despite negative health and social consequences, and withdrawal symptoms when access to alcohol is prevented . Ethanol exerts its toxicity through changes to multiple neurotransmitter systems, including serotonin, dopamine, gamma-aminobutyric acid, glutamate, acetylcholine, and opioid systems. These neurotransmitter imbalances result in dysregulation of brain circuits responsible for reward, motivation, decision making, affect, and the stress response.

Previous clinical trials have tested single and multiple doses of noribogaine in healthy individuals and opioid-dependent patients. In healthy subjects (Study ZPS-468, ACTRN1261000821897), doses from 3 to 60 mg were well tolerated with minor adverse events such as headaches and nosebleeds. Opioid-dependent patients (Studies ZPS-513, ACTRN12613001064796; DMX-100, UTN U1111-1159-4757) received higher doses (60 - 180 mg) and reported adverse events including nausea, headache, and anxiety. These could be related to opioid withdrawal or noribogaine itself. Importantly, no serious adverse reactions were observed in any trial.

Single oral administration of noribogaine shows that the drug reaches peak levels in the bloodstream within 2 - 4 hours depending on the dose, with a half-life of 24 - 50 hours. The dose and its effect on blood levels increased proportionally in healthy subjects (Studies ZPS-468). An increase in the QT interval on electrocardiograms was observed in all studies, which warrants further investigation, especially considering the presence of opioids in some studies.

Overall, these trials suggest that noribogaine can be safely administered orally at various doses and has the potential for long-acting effects in addiction treatment.

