AE = adverse event; BMI = body mass index; C-SSRS = Columbia-Suicide Severity Rating Scale; ECG = electrocardiogram; FSH = Follicle Stimulating Hormone; HCG = Human Chorionic Gonadotrophin; HIV = Human Immunodeficiency Virus, IMP = investigational medicinal product; MEQ30 = Mystical Experience Questionnaire; PK = pharmacokinetic.

a Written consent prior to the Screening window is permitted.

b Update only.

- c FSH testing is required for post-menopausal women only.
- d Serum β-HCG testing is required for women of childbearing potential (WOCBP) only.
- e Participants will be administered noribogaine or placebo capsules at H0 and H12 from D1 to D7 with a final dose on D8 at H0.
- f Participants will fast for at least 8 hours before the morning dose until at least 4 hours after dosing on all days. Participants will fast for 3 hours before the evening dose until 2 hours after dosing on all days except for Day 1 where they will fast for 3 hours after dosing. Planned D1 meal times will be followed on D-1. For all other doses participants will fast for at least 2 hours before the dose until at least 3 hours after the dose. For non-dosing days, meals will be provided at standard unit times. See [Table 3](#) for scheduled meal timepoints. Participants will refrain from consuming water from 1 hour pre-dose until 1 hour post-dose. Chilled water is not permitted on Days -1, 1 and 8 due to interference with intensive cardiac assessments.
- g Respiratory Rate, Oxygen Saturation, Tympanic Temperature, Blood Pressure and Heart Rate. Participants will be supine for a minimum of 5 minutes prior to measurements. See [Table 3](#) for Treatment Period timepoints.
- h Participants will be supine for a minimum of 10 minutes prior to measurements. See [Table 3](#) for Treatment Period timepoints.
- i 24-hour Holter ECG performed at Screening . Telemetry will be performed from at least H-24 on D-1 to H16 on D8.
- j Samples to be obtained at H0.
- k Procedure to be performed at H6.
- l See [Table 3](#) for Treatment Period timepoints.
- m Pooled urine collection will be performed H0 - 6, 6 - 12 and 12 - 24 hours post first dose on Day 1, and at H0 - 6, 6 - 12, 12 - 24, 24 - 36, 36 - 48, and 48 - 72 post last dose on Days 8 - 10. Predose sampling is to be performed within 30 minutes prior to dosing.

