4.13.2 Dose Linearity Analysis

Dose proportionality of noribogaine pharmacokinetics will be evaluated using a power model regression approach, as recommended by FDA and EMA guidelines. The following PK parameters will be assessed across different dose levels: C_{max} , AUC_{0-12} , AUC_{0-24} , and AUC_{0-inf} .

The log-log regression model will be applied using the following equation:

$$\log(\text{PK Parameter}) = \beta_0 + \beta_1 \log(\text{Dose}) + \epsilon$$

where β_1 (slope) represents the dose proportionality exponent. Dose proportionality will be concluded if β_1 lies within the acceptance range of 0.75–1.25 and its 90% confidence interval (CI) includes 1.

To further support the assessment, descriptive statistics for dose-normalized PK parameters (C_{max}/Dose and AUC/Dose) will be presented.

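### SAP Table 5 asks for terminal-phase parameters on Day 1, where re-dosing at 12 h leaves about 71–85% of AUC0-inf extrapolated against the SAP's own 20% limit

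*SAP*

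**What the plan says.** SAP section 4.13, Table 5, assigns five terminal-phase quantities to Day 1 as well as Day 8:

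- the half-life row reads "Terminal elimination half-life (Day 1 and Day 8";
- lambda_z is to be fitted "using at least three time-points during the terminal elimination phase (Day 1 and Day 8";
- AUC0-inf is the "Area under the plasma concentration-time curve from time 0 extrapolated to infinite time (Day 1 and 8";
- %AUCextrap and Vz/F carry the same two days, and Vz/F is defined as Dose/(lambda_z × AUC0-inf).

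CL/F is planned for Day 8 only, as Dose/AUCtau.

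Below the table, the SAP sets three conditions for lambda_z and AUC0-inf: at least three points after Cmax, adjusted R-squared of at least 0.8, and "AUCextrap < 20" per cent. Values that fail are flagged. They may be left out of the summaries, as the sponsor decides with the pharmacokineticist's input.

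Section 4.13.2 puts AUC0-inf, with Cmax, AUC0-12 and AUC0-24, into the power model ("The following PK parameters will be assessed across different dose levels") without naming a day. The list of dose-normalised parameters names none either.

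In the protocol, footnote e of the Schedule of Assessments gives "capsules at H0 and H12 from D1 to D7 with a final dose on D8 at H0". Section 1.1 reports a peak at 2–4 h after a single oral dose, "with a half-life of 24 - 50 hours".

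**The concern.** The single-dose profile on Day 1 ends at H12, when the next dose is given. With a peak at 2–4 h, 8–10 h of decline are observed. That is 0.16 of a half-life at worst (8/50) and 0.42 at best (10/24), too little to identify a terminal phase.

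Half-life, AUC0-inf and Vz/F are among the primary PK endpoints. As planned, the Day 1 values are either nearly all flagged and dropped, or kept by a discretionary decision and summarised. If they are kept, a short Day 1 half-life beside a sound Day 8 half-life would look like time-dependent kinetics, when the sampling window produced it. A Day 1 AUC0-inf that is mostly extrapolation could also enter the dose-proportionality test, since no day is named there.

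**Working it through.** The documents state no expected extrapolated share, so there is no planned figure to reproduce.

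**Inputs from the documents.** Half-life T = 24–50 h and Tmax 2–4 h (protocol 1.1). Second dose at H12 and last dose on Day 8 at H0, so 15 doses (footnote e). Day 1 plasma samples at 1, 1.5, 2, 2.5, 3, 3.5, 4, 6, 8 and 12 h; last sample at H168 on Day 15 ± 2 days, i.e. from H120 (Schedule of Assessments). Limits of 20% and 0.8 (SAP 4.13). Write k = ln 2/T.

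**1. Day 1 extrapolated share, one-phase decline.**

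- To H12: exp(−12k) = 2^(−12/T). T = 24 h gives 70.7%; T = 50 h gives 84.7%.
- With first-order absorption set to a Tmax of 2 or 4 h: 71.7–73.1% and 85.1–85.7%.
- Over 0–24 h with both doses: [exp(−12k) + exp(−24k)]/2. T = 24 h gives (0.707 + 0.500)/2 = 60.4%; T = 50 h gives (0.847 + 0.717)/2 = 78.2%.
- To reach 20% at H12, the fitted half-life would have to be 12/log2(5) = 5.2 h, far below 24 h.

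**2. Half-lives that pass the fit check.** This step needs a residual error, which the documents do not give; 5–20% CV was assumed. The SAP rules were simulated on the Day 1 sampling times, taking the post-Cmax window with the best adjusted R-squared. There were 36 one-compartment settings (T 24, 37 and 50 h; Tmax 2, 3 and 4 h; CV 5, 10, 15 and 20%), with 4,000 profiles each. Between 11% and 76% of profiles reached adjusted R-squared 0.8. Median half-life among those, across the Tmax values:

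| True half-life | CV 5% | CV 10% |
|---|---|---|
| 24 h | 22.0–24.1 h | 16.8–18.5 h |
| 50 h | 34.6–37.2 h | 21.9–24.6 h |

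At 5–10% error this runs from no bias (24.1 against 24 h) to (50 − 21.9)/50 = 56% short. The median was below the truth in 35 of 36 settings. The reason is selection: with so little decline to see, mainly steep slopes pass the check. In every setting, at most 0.2% of the profiles that passed also had an extrapolated share below 20%, which is under 0.1 of the 48 active participants.

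**3. What Day 8 can deliver.** After the last dose the extrapolated share is exp(−k × t_last):

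| Last quantifiable sample | T = 24 h | T = 50 h |
|---|---|---|
| H168 | 0.8% | 9.7% |
| H120 (follow-up on Day 13) | 3.1% | 18.9% |
| H72 (follow-up sample below LLOQ, hence omitted) | 12.5% | 36.9% |

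**4. Vz/F on Day 8.** After 15 doses at 12 h intervals, AUC from the last dose to infinity, relative to a single dose, is (1 − exp(−180k))/(1 − exp(−12k)):

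- T = 24 h: 0.9945/0.2929 = 3.4.
- T = 50 h: 0.9175/0.1533 = 6.0.

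Dose/(lambda_z × AUC0-inf) with one dose in the numerator would therefore be too low by a factor of 3.4–6.0. AUCtau on Day 8 is 1 − exp(−180k) of the single-dose AUC0-inf, i.e. 99% (24 h) to 92% (50 h), so Dose/(lambda_z × AUCtau) is nearly right.

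**The case against.** **The SAP foresees such failures.** It flags them, lists the dependent parameters with them, and allows exclusion. A value with 71–85% extrapolation would be flagged, and the misleading comparison between days arises only if flagged values are kept. This limits the harm but does not remove it. Exclusion is optional, and section 4.13.1 sets to missing only parameters that cannot be calculated.

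**Little else depends on these values.** Day 1 Cmax and AUC0-12, the accumulation ratios, CL/F and the concentration-QTc model do not use Day 1 lambda_z. The endpoint text gives no day for half-life or Vz/F. This stands and lowers the severity.

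A reader might also go further than the documents allow:

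- *Every Day 1 value must breach 20%.* This is close to true for one-phase decline at 24–50 h, but not certain for each participant. With an assumed dominant distribution phase, up to about a third of the profiles passing the fit check fell below 20%. They did so because their fitted half-life was about 5 h, so they were the most biased.
- *Day 1 half-lives are known to be biased short.* The direction is a tendency, and its size rests on an assumed error. At 24 h and 5% error the median is 0–8% short.
- *Day 8 supplies all five parameters as they stand.* It supports lambda_z and half-life. Day 8 AUC0-inf is not a single-dose exposure, and Vz/F needs another formula.

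**Conclusion.** The point holds, as a should-fix. From the documents' own half-life and dosing interval, and assuming one-phase decline, 71–85% of Day 1 AUC0-inf is extrapolated (60–78% over 0–24 h). That is about 3.5–4.2 times the SAP's limit, so essentially all active participants would fail it. A check that nearly everyone fails no longer separates good values from bad; it leaves a discretionary choice about what enters the summaries of primary PK endpoints.

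Short Day 1 half-lives are a likely further effect, ranging from none to more than 50% under an assumed 5–10% residual error. It would go too far to conclude that the half-life endpoint is lost: the profile after the last dose recovers it. That profile meets the 20% limit with a quantifiable sample at H120 or later, but not for long half-lives if H72 is the last quantifiable sample.

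**What to change.** - **Table 5:** delete Day 1 from lambda_z, t1/2, AUC0-inf, %AUCextrap and Vz/F. Estimate lambda_z and t1/2 only from the profile after the last dose (Day 8 to follow-up). Keep Cmax, Tmax, C12 and AUC0-12 as Day 1 parameters.
- **Vz/F:** define it on Day 8 as Dose/(lambda_z × AUCtau), consistent with the SAP's CL/F formula. State that Day 8 AUC0-inf includes carry-over and is not a single-dose exposure.
- **Section 4.13.2 and the dose-normalised list:** name the day for each parameter, drop Day 1 AUC0-inf, and assess dose proportionality on Cmax and AUC0-12 for Day 1 and for Day 8.
- **Long half-lives:** keep the 20% check on Day 8, and report how many participants have H72 as their last quantifiable sample.

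The cost is SAP wording only, with no new samples or visits. No Day 1 half-life would be reported, but the design cannot deliver one.

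### SAP 4.13 lists CL/F as dependent on λz although Table 5's formula does not use it, so a fully observed Day 8 value of a primary endpoint can be left out of the summaries

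*SAP*

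**What the plan says.** CL/F is among the primary PK endpoints in Protocol section 2 and SAP 2.2. SAP 4.13, Table 5, gives its calculation for Day 8 only: "Plasma clearance after extravascular administration calculated as Dose/AUC", where the AUC is that over tau. In the same table, Vz/F does have λz in its formula.

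Below Table 5, SAP 4.13 sets three conditions for λz and AUC0-inf: at least three terminal points excluding Cmax, "The Adjusted R-squared should be ≥ 0.8", and "AUCextrap < 20" per cent. If they are not met, the parameter is flagged, "together with those dependent on λ_z , such as" t1/2, CL/F and Vz/F, "and they may be excluded from the summary statistics". On who decides, it says: "The decision to include these parameters will be based on the decision of the Sponsor with input from the pharmacokineticist". It gives no rule for that decision and does not say whether a flag raised on one day affects parameters of the other.

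**The concern.** The conditions judge the quality of the terminal fit and of the extrapolation to infinity. CL/F as defined uses neither. A value from a complete Day 8 profile could therefore be left out of the summary because of a problem in a different part of the curve. The list would suit a clearance computed from AUC0-inf, which is not how Table 5 defines it.

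At stake is the number of participants, at most 12 on active drug per dose, who contribute to the summary of a primary endpoint. The choice would be made case by case with no stated criterion. One of the conditions, extrapolated AUC, is tied to slow elimination. If exclusions follow that condition, those left out would tend to have long half-lives and low clearance, and the summarised CL/F could be too high.

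**Working it through.** The plan states no figure to reproduce here. The check is first textual, then numerical.

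**1. Is the Day 8 AUC over tau observed?** Doses are about 12 h apart (SAP 3.1, Table 1), so tau is taken as 12 h. The Schedule of Assessments has Day 8 plasma samples at H0, at nine times from H1 to H8, and at H12. No extrapolation is needed, so the λz conditions do not test this AUC.

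**2. When does the extrapolation condition fail on Day 8?** Inputs:
- half-life 24–50 h, from single oral doses (Protocol 1.1);
- last sample 168 h after the last dose (Day 15 ± 2 days, so 120–216 h);
- the sample before it at 72 h (Day 11).

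For a single-exponential decline, the extrapolated fraction is about 2^(−t_last/t½). Setting it to 0.20 gives t½ = t_last/log2(5) = t_last/2.32. Hence 72/2.32 = 31 h, 120/2.32 = 52 h and 168/2.32 = 72 h.

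A one-compartment oral model agrees (absorption rate 1.5/h is an assumption; 15 doses every 12 h, the protocol's sampling times, the SAP's linear/log trapezoidal rule):

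| Last usable sample | Half-life at which 20% is reached | Extrapolated at 24 h | at 36 h | at 50 h |
|---|---|---|---|---|
| 72 h (follow-up missing or below LLOQ) | 30.9 h | 12.6% | 25.1% | 36.9% |
| 120 h (Day 13) | 51.6 h | 3.1% | 10.0% | 19.0% |
| 168 h (planned) | 72.3 h | 0.8% | 3.9% | 9.8% |
| 216 h (Day 17) | 93.0 h | 0.2% | 1.6% | 5.0% |

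**3. What could exclusion do to the summary?** This simulation assumes that 24–50 h spans ±2 SD or ±1 SD of log half-life, that clearance carries 50% or 100% of that variance, that every participant has the same last sample, and that everyone at or above 20% is excluded:

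| Last sample | Share failing | At least one of 12 fails | Geometric mean CL/F, retained / all |
|---|---|---|---|
| 168 h | 0–2% | 0–23% | 1.00–1.015 |
| 120 h | 1–13% | 14–82% | 1.002–1.07 |
| 72 h | 62–73% | about 100% | 1.10–1.39 |

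The last row is a bounding case, since it supposes that nobody has a usable follow-up sample.

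**4. Day 1.** Table 5 also asks for λz, AUC0-inf and extrapolated AUC on Day 1, where only 12 h are seen before the next dose. The same model gives 72–86% extrapolated for half-lives of 24–50 h, so every participant fails. If flags are not confined to their own day, a literal reading could flag Day 8 CL/F for everyone.

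**5. Steady state.** Dose/AUCtau equals CL/F only at steady state. There are 2 × 7 + 1 = 15 doses. In a one-compartment approximation, Day 8 AUCtau reaches 1 − 2^(−15 × 12/t½) of its steady-state value:
- t½ 50 h: 1 − 2^(−3.6) = 0.9175, so CL/F is overstated by 1/0.9175 − 1 = 9%;
- t½ 72 h: 1 − 2^(−2.5) = 0.8232, so by 1/0.8232 − 1 = 21%.

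**The case against.** A reader might infer that the SAP systematically removes slow eliminators and so biases CL/F upward. The documents do not support that:
- Exclusion is optional, and SAP 4.13.1 lists PK parameters for each participant, so an omission would be visible.
- With planned sampling, half-lives of 24–50 h pass the extrapolation condition, even at a Day 13 visit (19.0% at 50 h).
- The adjusted R-squared and three-point conditions have no stated link to half-life.
- The direction could reverse. Values below LLOQ after Cmax are dropped. A participant with low exposure and a 35 h half-life who falls back to the 72 h sample would have 2^(−72/35) = 24% extrapolated and fail, while a slower eliminator with a measurable 168 h sample passes. The LLOQ is not given, so this cannot be sized.

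Two further points deserve weight. Within a fixed-dose cohort, geometric mean CL/F equals dose divided by geometric mean AUC0-12 (tau of 12 h), and AUC0-12 is summarised free of the λz rule. CL/F is also descriptive only: no test uses it and the dose-proportionality model omits it. Second, a long half-life does bear on CL/F, because steady state may not have been reached.

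All of this limits the consequence. It does not justify the rule. The AUC0-12 summary would show the information but leave two linked primary-endpoint tables resting on different participants. The steady-state shortfall is a matter for a footnote; terminal fit and extrapolation conditions do not measure it.

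**Conclusion.** The contradiction is certain and needs no assumption: CL/F as defined does not depend on λz, yet the SAP treats it as if it did and leaves its inclusion to the Sponsor's discretion.

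The numerical consequence is conditional. With complete follow-up at 168 h and half-lives of 24–50 h, exclusion for extrapolation should be rare and the effect on geometric mean CL/F about 0–1.5%. A Day 13 visit puts the limit just above the range (52 h) and the effect at 0.2–7%. A missing or unquantifiable follow-up sample puts the limit inside the range, at about 31 h, and there the loss could be large. These sizes rest on the one-compartment model, the assumed spread of half-life and clearance, and exclusion of every failing participant. The half-life after multiple dosing is not given and could differ from the single-dose range. The supportable conclusion is that the rule can exclude valid data and, where extrapolation is the cause, could raise summarised CL/F. It does not follow that it will.

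**What to change.** In SAP 4.13:
- Delete CL/F from the list of λz-dependent parameters.
- State that Day 8 CL/F, with tau given as 12 h, is summarised for every participant with an evaluable Day 8 AUC0-12, whatever the λz flags.
- Apply the λz flags separately for Day 1 and Day 8, and only to λz, t1/2, AUC0-inf (with its dose-normalised form) and Vz/F.
- Footnote the CL/F summary: Dose/AUCtau assumes steady state, and in a one-compartment approximation CL/F is overstated by roughly 9% at a 50 h half-life and by more at longer half-lives.

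The cost is SAP wording only. No sample, visit or extra analysis is needed.
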